**Table 1b - Schedule of Study Activities for the Control arm (CMM)**

[X] Optional activity.

\*For subjects consented prior to the EC approval of the revised consent, they may be reconsented at any study visit.

DTM INT-2020PM2 Rev B 21-Aug-2020  
Confidential

## B.9.2. Statistical Analysis

Descriptive statistics will be used to summarize baseline and outcome data collected during the study. Continuous variables will be summarized using means, standard deviations, and ranges. Categorical variables will be summarized in frequency distributions.

### B.9.2.1 Primary Analyses

The *primary efficacy endpoint* will be evaluated with a Pearson Chi-square binomial test for superiority at the two-sided 0.05 alpha level.

$H_0$ : The percentage of subjects (P) who achieve a 50% improvement in their back VAS pain score at 6 months in the Test group is the same as in the Control group.

$$P_{\text{Test}} = P_{\text{Control}}$$

$H_1$ : The percentage of subjects (P) who achieve a 50% improvement in their back VAS pain score at 6 months in the Test group is superior to that in the Control group.

$$P_{\text{Test}} \neq P_{\text{Control}}$$

### B.9.2.2 Secondary Analyses

The following *secondary endpoints* will be evaluated:

- If the primary efficacy endpoint in the test group is found to be superior to that in the control group, then a secondary endpoint will evaluate whether the proportion of subjects who achieve a 50% improvement in their back pain VAS score at 1, 3, 9, 12, 18 or 24 months in the test group is superior to that in the control group. A superiority test based on the difference in proportions will be performed based on the following null hypothesis, with a two-sided p-value of 0.05 or less considered evidence of statistical significance.

$H_0$ : The proportion of subjects (P) who achieve a 50% improvement in their back pain VAS score at 1, 3, 9, 12, 18, or 24 months in the Test group is less than or equal to that in the Control group.

$$P_{\text{Test}} = P_{\text{Control}}$$

$H_1$ : The proportion of subjects (P) who achieve a 50% improvement in their back pain VAS score at 3 months in the Test group is greater than that in the Control group.

$$P_{\text{Test}} \neq P_{\text{Control}}$$

- Change in mean VAS will be evaluated with two-sample t-test of non-inferiority in means with a 0.65 cm non-inferiority margin at 6 months.

$H_0$ : The change (C) in subject's VAS pain intensity score relative to baseline at the Primary Efficacy Assessment in the Test group is worse than that of subjects in the Control group by more than 0.65 cm.

$$C_{\text{Test}} \geq C_{\text{Control}} + 0.65 \text{ cm}$$

$H_1$ : The change (C) in subject's VAS pain intensity score relative to baseline at the Primary Efficacy Assessment in the Test group is no more than 0.65 cm worse than the mean change from baseline in the control group.

$$C_{\text{Test}} < C_{\text{Control}} + 0.65 \text{ cm}$$

The non-inferiority margin of 0.65 cm was selected based on a previous study of a similar therapy against traditional SCS. In that study, the experimental therapy showed a 4.9 point improvement while traditional SCS showed a 3.6 point improvement for a difference of 1.3 points. Taking 50% of this treatment effect yields the margin of 0.65 cm. If the null hypothesis is successfully rejected for the non-inferiority test, a test for superiority of treatment to control will be performed based on a two-sided 0.05 alpha level.

The following secondary endpoints do not have an associated hypothesis, and no significance level will be assigned to statistical tests that may be performed.

Analysis of results through 6 months will be based on the mITT population. For time points after 6 months where crossover is allowed, crossover subjects will be counted as failures (i.e. non-responders) for endpoints defined in terms of responders, carrying forward the baseline (pre-treatment). Sensitivity analysis of both secondary endpoints will also be performed to where crossover subjects are censored at the point of crossover.

- Comparison of Back Pain Treatment Success (responder rate), measured as subjects with at least a 50% reduction in Back Pain VAS, between test and control
- Comparison of mean change from Baseline in Back Pain VAS, between test and control
  - Repeated measures models will be used to produce estimates for these two secondary endpoints, with graphical presentation of the responder rates and mean changes from baseline.

#### **B.9.2.4 Handling of Missing Data**

Missing data will be minimized by rigorous follow-up and investigator and site training. Additionally, for subjects in the DTM™ SCS arm who do not have a successful Trial Phase, results from the Trial Phase will be utilized for the primary endpoint as described in Section B.7.2. Effectiveness Assessment Definitions. In case of missing data Mixed Model for Repeated Measures (MMRM) will be used to produce estimates. Additionally, sensitivity analyses for missing data will be performed. Unless otherwise specified, all other analyses will be based on the evaluable data with no imputation.

Details on these analyses will be provided in a separate statistical analysis plan.

## C. Risk Analysis

### C.1. Description and Analysis of All Increased Risks to Subjects

#### ***Spinal Cord Stimulation (SCS) Risks:***

The DTM™ SCS programming approach will be used with commercially available, US FDA approved, CE marked Intellis™ SCS system within approved indications for use. Anticipated potential adverse events resulting from the study are expected to be in line with adverse events already documented for SCS using a standard programming approach.

There are known risks associated with the use of any SCS system. Known risks are associated with the implant procedure, the stimulation, the implanted device (not associated with stimulation) and external devices such as the charger and remote control. These are typical of commercial SCS systems. Subjects will be informed of these anticipated risks in the study consent process.

#### **Risks of Surgery**

Implanting a neurostimulation system has risks similar to spinal procedures, including spinal fluid leak (spinal fluid collection under the skin), headaches, swelling, bruising, bleeding, infection, or paralysis.

Subjects on anticoagulation therapy may be at higher risk for problems after surgery such as hematomas that could result in paralysis.

#### **Spinal Cord Stimulation Risks**

The implantation of a spinal cord stimulation system involves risks that are similar to other spinal procedures. In addition to those normally associated with surgery, implantation or use of a neurostimulation system includes, but is not limited to, the following risks:

- Allergic or immune system response to the implanted materials
- Infection
- Lead or neurostimulator erosion through the skin or migration
- Leakage of cerebrospinal fluid
- Loss of pain relief may return patients to their underlying pain condition
- Persistent pain at the neurostimulator site
- Placement of the epidural lead is a surgical procedure that may expose patients to risks of epidural hemorrhage (bleeding), hematoma, or paralysis
- Radicular chest wall stimulation
- Seroma (fluid collection in pocket where stimulator is placed) or hematoma at the neurostimulator site
- Change in stimulation, possibly related to cellular changes around the electrode(s), shifts in electrode position, loose electrical connections, lead fractures, which has been described by some patients as uncomfortable stimulation (jolting or shocking sensation)

- Over time there could be changes in the level of symptom control. In most cases, the physician can correct these changes without surgery.
- Formation of excessive tissue around the lead in the epidural space can result in delayed spinal cord compression and paralysis, requiring surgical intervention. Time to onset can range from weeks to many years after implant.
- The safety of this therapy is unknown for pregnancy, unborn fetus, or delivery
- Stimulation-dependent gastrointestinal symptoms such as diarrhea, incontinence or constipation
- Stimulation-dependent bladder symptoms such as urinary retention, incontinence or frequency
- Unexpected changes in stimulation - Electromagnetic interference, changes in posture, and other activities can cause a perceived increase in stimulation

## **System Revision Risk**

The Intellis™ Neurostimulator may require replacement in 9 years or earlier, regardless of the number of times the neurostimulator is recharged. It is possible that the system will need to be revised (explanted, replaced, or repositioned) earlier than 9 years. Possible reasons for revision/explant may include infection, malfunction, and migration of the system components. The risks associated with system revision are equivalent to other commercially available systems.

## **Pregnancy Risks**

Pregnant women are not able to take part in this study. Female subjects must agree to not become pregnant during the study by using a medically acceptable method of birth control. If a subject becomes pregnant during this study, there may be risks to the unborn child that are not yet known. Subjects will be advised and encouraged to notify the study doctor immediately if they think they are or have become pregnant. Subjects that become pregnant during the study will be instructed to turn the neurostimulator “OFF” and will be exited from the study.

## **Radiographic Imaging**

As part of the study, subjects may be required to have fluoroscopic or X-ray images taken of their thoracic spine in addition to the imaging conducted to implant the leads. This may be beyond what is standard of care. The risk associated with these additional images has been considered and determined to be minimal since the total radiation dose will be approximately the same as one CT scan of the abdomen.

## **Study Risk Control Measures**

The following will be done to mitigate risks associated with the implanted system:

- Investigators who are experienced with spinal cord stimulation implantation techniques will be utilized
- Instructions will be given to the study participants to ensure they can properly use the patient programmer and recharger system
- Subjects can turn off stimulation at any time during the study with the patient programmer or recharger

- Periodic monitoring of the study participants
- Written materials that contain precautions, warnings, and contraindications, as well as instructions on the use of the devices will be available and/or provided to the clinicians and subjects

Since the efficacy measure in this study is intensity of pain in the back and legs, pain in these areas does not need to be reported as an adverse event unless it meets the definition of a serious adverse event. However, Investigators may, at their discretion, report any other pain-related adverse events during the study.

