#### Definitions

An **Adverse Event** (AE) is any untoward medical occurrence defined as an unintended disease or injury or untoward clinical signs (including abnormal laboratory findings deemed clinically significant as determined by the investigator) in a subject whether or not related to the investigational or commercial medical device. This definition includes events related to the study medical devices and events related to the study procedures. An AE is also any event related to any underlying medical condition, present at Baseline, which increases in severity by a clinically meaningful amount during the study as determined by the Investigator.

For all adverse events, the Investigator will provide an assessment of the adverse event, its severity, treatment/intervention provided, relationship to the device/procedure, and resolution.

As the primary efficacy measure in this study is pain, back or leg pain does *not* need to be reported as an adverse event unless it meets the definition of a serious adverse event. However, Investigators may, at their discretion, report any pain-related adverse events during the study.

Pre-existing conditions will not be reported as an adverse event unless there has been a substantial increase in the severity or frequency of the problem which has not been

attributed to natural history.

**A Serious Adverse Event (SAE)** is an adverse event that

- Led to death
- Led to serious deterioration in the health of the subject, that either resulted in
  - a life-threatening illness or injury (life-threatening is defined as at risk of death at the time of the event), or
  - a permanent impairment of a body structure or a body function, or
  - in-patient hospitalization or prolongation of existing hospitalization (in-patient hospitalization is defined as a hospital admission for a period of greater than 24 hours), or
  - medical or surgical intervention to prevent life-threatening illness or injury or permanent impairment to a body structure or a body function,
- Led to fetal distress, fetal death, or a congenital abnormality or birth defect

Those known adverse events related to the device, procedure or therapy are listed in the Risk Analysis Section C.

**A Serious Adverse Device Effect (SADE)** is an adverse device effect that has resulted in any of the consequences characteristic of a serious adverse event.

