## **Reporting**

All device or procedure-related adverse events will be captured from enrollment through the completion of the study on the Adverse Event Case Report Form (CRF). However, in accordance with ISO 14155 latest version when using commercial medical devices, device deficiencies, SAEs, SADEs and USADEs must be reported per the post-market surveillance/vigilance system of the manufacturer as specified in the manufacturer's labeling/manuals.

All AEs, Device Deficiencies, SAEs, SADEs and USADEs (see list in section C) reported during the study will document severity, treatment/intervention provided, relationship to the device/procedure, and resolution. Any USADEs and/or deaths occurring during the study procedures will also be evaluated to determine whether the SCS system might have malfunctioned, or caused or contributed to the event.

All SAEs/SADEs/USADEs will be documented and reported to SGX as soon as possible, but no later than 24 hours after becoming aware of the SAE.

The SGX contact information for these events is or reporting through eCRF:

E-mail: [[contact]](mailto:[contact])

The Investigator or site staff may report an event to the sponsor by email, telephone or fax initially, but must follow-up by completing an Adverse Event CRF. The monitored CRF should be sent to SGX and, if possible, be accompanied by copies of source documentation regarding the event (e.g., physician / nurse notes or summaries / hospitalizations records). The Investigator must also report the SAE to the EC according to their local regulations.

An attempt must be made by the Investigator/site staff to schedule a subject visit as soon as feasible following the report of the SAE. In the event of a subject death, all available information (e.g. autopsy or other post-mortem findings) should be provided on the CRF. An Investigator shall submit a report to the sponsor of any USADE occurring during the study as soon as possible, but in no event later than 10 working days after the Investigator first learns of the effect. SGX will conduct an evaluation of the event to determine whether the event is an anticipated event based on labeling and risk analysis. The Investigator must also report the event to the EC if it is determined to be unanticipated.

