### **D.1.2.2. Surgical Accessories**

The surgical accessories that will be used in the study will be commercially available devices.

**Torque Wrench:** A commercially available Torque Wrench is used to tighten the screws that lock a percutaneous lead into the INS and/or a lead extension. It also tightens the screws that lock the lead extension into the INS when this is used.

**Lead anchors:** Lead anchors may be used to possibly prevent lead migration and/or lead strain. These are used to anchor the percutaneous leads to the supraspinous ligament or fascia. Lead anchors used in this study are commercially available (Medtronic, Minneapolis, MN) and designed to slide freely over the lead length to the required fixation position. Surgical sutures are then tied around the anchor clamping the sleeve in place on the lead.

**Insertion Needle:** Percutaneous leads are implanted in the dorsal epidural space using insertion needles. An insertion needle contains a cannula and stylet that facilitate access to the spinal canal for lead placement. The insertion needle is a 14G epidural needle with a thin wall and a modified Touhy non-coring tip. The cannula and stylet are designed to lock together and maintain the orientation of the tip of each component. The hub of the insertion needle has a standard luer fitting.

**Stylets:** Stylets are used to push and “steer” a percutaneous lead into the desired place within the epidural space. The distal end of the stylet could be straight or curved. The implanter is able to use either one in order to comfortably maneuver a percutaneous lead through the epidural space until it reaches the desired implant location.

**Tunneling Tool:** A Tunneling Tool is used to create a subcutaneous tunnel that directs the percutaneous leads or lead extensions from the midline incision to the leads from the INS implant site. This is a single use tool.

**INS Template:** The INS Template is an aid to be used for the implanter intended for proper sizing of the INS pocket within each subject.

**INS Port Plug:** An INS Port Plug is used to seal the port of the INS that is not in use when only one percutaneous lead is implanted.

**Lead Blank:** A Lead Blank is an optional aid made out of flexible stainless steel that has an outer diameter similar in size to the percutaneous lead. A lead blank can be optionally used to clear a path for the introduction of a percutaneous lead into the epidural space.

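### The reporting exemption for non-serious back or leg pain conflicts with the protocol's own adverse event definition and capture rule, so device- or procedure-related pain may be missing from the safety tables.

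*Protocol*

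**What the plan says.** The exemption stands in two places in the protocol. B.7.6 (Definitions) says that "back or leg pain does *not* need to be reported as an adverse event unless it meets the definition of a serious adverse event". C.1 (Study Risk Control Measures) says that "pain in these areas does not need to be reported as an adverse event unless it meets the definition of a serious adverse event". Both give the same reason: pain is what the study measures for efficacy.

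Each is followed by a sentence on discretion, and the two differ by one word. B.7.6: "However, Investigators may, at their discretion, report any pain-related adverse events during the study". C.1: "However, Investigators may, at their discretion, report any other pain-related adverse events during the study".

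Three other statements bear on the same events:

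- B.7.6 (Definitions) includes events related to the study devices and procedures in its definition of an adverse event. It adds: "An AE is also any event related to any underlying medical condition, present at Baseline, which increases in severity by a clinically meaningful amount during" this trial, in the investigator's judgement. A further rule makes a pre-existing condition reportable once it is substantially worse in severity or frequency, provided this is not put down to natural history.
- B.7.6 (Reporting): "All device or procedure-related adverse events will be captured from enrollment through the completion of the study", on the adverse event form. Pain is not carved out.
- C.1 (Spinal Cord Stimulation Risks) lists two risks that are themselves pain: return of the underlying pain when relief is lost, and "Persistent pain at the neurostimulator site".

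SAP 5.9 tabulates adverse events descriptively, overall, by type and by relatedness. It has no separate rule for pain.

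**The concern.** The exemption is drawn by body area and seriousness. Its two sentences do not distinguish the patient's index pain from pain that the device or the surgery has caused. In this trial the surgery is on the back. D.1.2.2 describes tunnelling from a midline incision and says of the lead anchors: "These are used to anchor the percutaneous leads to the supraspinous ligament or fascia". Non-serious pain from the incision, an anchor or a lead site is therefore back pain, and on its face it falls under the exemption.

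Documenting safety is a stated objective (B.2). If some sites follow the exemption and others the capture rule, the reported rate of this harm depends partly on how each site reads the protocol. The loss would not be even between arms, because before the 6-month crossover only the test arm has trial and permanent implant procedures.

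**Working it through.** No arithmetic applies. The plan states no figure on this point, and no rate of procedure- or device-related pain appears from which to derive one. The check is to put each kind of non-serious pain against each rule.

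| Non-serious event | Exemption (B.7.6 Definitions; C.1) | Adverse event definition (B.7.6) | Capture rule (B.7.6 Reporting) |
|---|---|---|---|
| Back pain from an incision, lead or anchor | Need not be reported | Is an adverse event | Must be captured |
| Index back or leg pain, meaningfully worse than baseline | Need not be reported | Is an adverse event | Must be captured if judged device- or procedure-related |
| New back or leg pain, not judged related | Need not be reported | Falls under the general definition | Silent |
| Pain at the neurostimulator site | Exempt only if the site counts as back | Is an adverse event | Must be captured |

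**Precedence.** In the first two rows the rules give opposite instructions. No section says which prevails. The exemption is the only text specific to back and leg pain, so a site can reasonably treat it as overriding the general rules. Another site can as reasonably treat the capture rule as absolute.

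**Discretion.** It does not settle the matter, because it permits a report without requiring one. The word added in C.1 makes matters less clear: it can be read as making even pain outside the back and legs optional. That matters for the fourth row, since D.1.1 says only that the pocket is subcutaneous, not where it is.

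**Seriousness.** The exception is narrow. It needs death, threat to life, permanent impairment, admission of more than 24 hours, intervention to prevent such an outcome, or fetal harm. Persistent wound or anchor pain managed without admission could meet none of these.

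**Other data.** Pain VAS is collected for both back and leg (the B.8 section on the definition of success) and again at unscheduled visits (Table 1a footnote). A VAS score carries intensity. It carries no cause, relatedness, treatment or resolution, which are the attributes B.7.6 asks for on each adverse event. In a subject whose index pain has fallen, a lower back VAS can coexist with new anchor pain and would not reveal it.

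**Analysis.** SAP 5.9 works from reported events. What is not on the form is not in the tables by type or by relatedness.

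**The case against.** The best defence is that the exemption states its own purpose. It is tied to pain as the efficacy measure, so a natural reading confines it to the index pain, kept out of the event tables because it is already the outcome. On that reading device- and procedure-related pain stays reportable under the capture rule and nothing is lost. This is a fair account of what was probably intended. But neither sentence says so, and sites work from the words.

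The defence also limits the point in several ways, and these limits stand:

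- A reader might infer that the protocol has no rule at all for new, worsened or device-caused pain. That is true of the exemption sentences but not of the whole document. The fault is an unresolved contradiction.
- A reader might infer that neurostimulator-site pain is exempt. The documents do not place the pocket in the back or leg, so this cannot be said. Leg pain from a lead lying near a nerve root is likewise not described anywhere, and the point does not need it.
- A reader might infer that most device harm is hidden. Most risks listed in C.1, such as infection, cerebrospinal fluid leak, erosion or migration, hemorrhage and seroma, are not back or leg pain and remain reportable.
- Worsening index pain is not lost to the trial. It shows in VAS change and responder status in both arms. Requiring an adverse event form for it as well would partly count the efficacy outcome twice, so how to handle it is open to debate.
- Healthcare utilization, imaging for suspected lead migration (B.6.19) and explant counts (SAP 5.4) offer some indirect trace of device problems. None of them records pain as a harm with its cause.

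**Conclusion.** The point holds as a conflict between instructions. The exemption in B.7.6 (Definitions) and C.1 cannot be squared with the adverse event definition in B.7.6 or with the capture rule in B.7.6 (Reporting), and the plan does not rank them. The consequence is possible under-reporting of non-serious incision, anchor or lead-site back pain. It would fall mainly in the test arm before crossover, and afterwards also in control subjects who receive an implant.

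The size is unknown. One could assume an event rate and apply it to about 75 randomized test subjects (half of 150), but any such rate would be invented. Moreover, 75 is not the denominator of the main tables: SAP 5.9 uses the mITT set, which leaves out some randomized test subjects, with ITT only as a sensitivity analysis.

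The conclusion assumes that at least some sites would read the exemption literally. The primary endpoint is not affected. The change should be made because it protects a stated objective at low cost.

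**What to change.** Reconcile the three places (B.7.6 Definitions, B.7.6 Reporting, and C.1):

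1. Limit the exemption to the pre-existing index back or leg pain that the VAS already measures.
2. State that back or leg pain is always recorded on the adverse event form, in both arms, when it is new in location or character or is judged device- or procedure-related. Name pain at an incision, lead, anchor or neurostimulator site as included.
3. State how worsening of the index pain is handled, so that the exemption agrees with the adverse event definition.
4. Use one wording for the discretion sentence, so that it cannot be read as making other pain reports optional.
5. In SAP 5.9, give device- or procedure-related pain its own line in the tables.

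This alters recording and analysis only. It costs a short protocol amendment, which under E.6 needs sponsor, ethics committee and investigator approval, with matching form instructions and a SAP edit. Sites will complete some extra adverse event forms, and the test arm's reported event rate may look slightly less favourable.
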